### **2.3 Co-Primary Endpoints**

Two co-primary endpoints are defined: dominant hand (DH) upper-limb performance on the TRG Essential Tremor Rating Assessment Scale (TETRAS), and the Bain & Findley Activities of Daily Living (ADL) scale. Statistical testing of each primary endpoint will be based on the cohort of all enrolled and treated subjects for whom outcome data are available.

The statistical objective related to each primary endpoint is to demonstrate that essential tremor is reduced from baseline under treatment with the Cala TWO device. Formally, the null and alternative hypotheses to be tested for each primary endpoint are as follows:

$$\begin{aligned} H_0: \mu_T &\geq 0 \\ H_A: \mu_T &< 0 \end{aligned}$$

where  $\mu_T$  is the raw change in the rating score from pre-stimulation at baseline to post-stimulation at three months in the endpoint in question.

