| Safety Endpoint | The safety of the Cala TWO device will be evaluated by the incidence of device and therapy-related adverse events. Additionally, all adverse events documented during study conduct will be tabulated and reported. |

| | |
|---------------------|--|
| Number of Subjects | Up to 500 subjects |
| Number of Sites | Up to 40 US sites |
| Study Participation | The length of study participation is 3 months +/- 2 weeks |
| Follow-up Schedule | Enrolled subjects will return to the site at 1 month +/- 1 week and 3 months +/- 2 weeks from enrollment |

| Subject Population | |
|--------------------|--|
| Inclusion Criteria | 
Prospective subjects must meet all of the following criteria to be eligible for study participation:
 
 • Must be ≥ 22 years of age • Competent and willing to provide written, informed consent to participate in the study • A diagnosis of essential tremor as confirmed from clinical history and examination by a movement disorder neurologist • A tremor severity score of 2 or above in the dominant hand/arm as measured by any one of the TETRAS upper limb items and a minimum subset score of 6 across all upper limb items • Significant disability due to essential tremor (Bain & Findley score of 3 or above in any one of the upper limb items and a minimum subset score of 8 across all upper limb items) • Stable dose of tremor medications, if applicable, for 30 days prior to study entry • Stable dose of antidepressant medications, if applicable, for 90 days prior to study entry • Willing to comply with study protocol requirements including: 
 ○ remaining on a stable dosage of tremor and antidepressant medications, if applicable, during the duration of the study ○ no significant alcohol or caffeine consumption within 8 hours prior to study visits ○ no usage of the Cala TWO device within 8 hours prior to study visits |
| Exclusion Criteria | 
Prospective subjects who meet any of the following criteria are not eligible for enrollment in this study:
 
 • Moderate to severe ethanol dependence as defined by the criteria outlined in the DSM-5 (score of 4 or higher) |

- Implanted electrical medical device, such as a pacemaker, defibrillator, or deep brain stimulator, or implanted metal in the wrist to be stimulated

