## 2 STATISTICAL METHODS

### 2.1 General Principles

- All hypothesis testing will be performed using a two-sided test at a 0.05 level of significance or a one-sided test at a 0.025 level of significance. P-values will be rounded to three decimal places. If a p-value is less than 0.001 it will be reported as “< 0.001.”
- Summary statistics will be reported for all analyzed variables.
  - Continuous data will be summarized using descriptive statistics: mean, standard deviation, median, and interquartile range (first and third quartiles).
  - Categorical, non-ordered variables will be summarized using frequency counts and percentages.
  - Ordinal variables, including those specific to study outcomes – e.g., the TRG Essential Tremor Rating Assessment Scale (TETRAS) and the Bain & Findley Activities of Daily Living (ADL) scale -- will be summarized using measures of central tendency and variance as opposed to frequency counts and percentages; that is, these variables will be reported using the same metrics as defined above for continuous variables.
- For events which can occur more than once in a single subject (e.g., adverse events), the percentage will be based on subjects experiencing the event, and both subject and event counts will be reported.
- Baseline is defined as the last measurement for the outcome of interest obtained before the exposure to study treatment.
- For time-to-event analyses, complete dates for events of interest (e.g., index treatment, outcome events, censoring), will always be used. Incomplete dates will be incorporated by defining the event as occurring on the earliest date possible given the incomplete information. E.g., a date of UNK-FEB-2018 will be incorporated into the analysis as 01-FEB-2018.
- Statistical analyses will be performed in SAS (SAS Institute, Cary, N.C.) version 9.3 or later, R (R Foundation for Statistical Computing, Vienna, Austria) version 3.2 or later, Matlab (The MathWorks, Inc., Natick, MA) version R2016B or later, Python (Anaconda, Inc., Austin, TX) version 3.6.6 or later, or in another validated statistical software package.

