### **2.7 Effectiveness Outcomes**

The effectiveness of the Cala TWO device in reducing essential tremor symptoms will be evaluated by the following:

Co-Primary Effectiveness Endpoints

---

- TRG Essential Tremor Rating Assessment Scale (TETRAS) subset score, relevant to the stimulated upper limb, raw change from pre-stimulation at baseline to post-stimulation at 3 months.
- Bain & Findley Activities of Daily Living (ADL) scale subset score, relevant to the stimulated upper limb, raw change from pre-stimulation at baseline to post-stimulation at 3 months.

These endpoints will be tested statistically using hypotheses as defined above and converted to percent tremor reduction as previously reported by Elble et. al. 2016.

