#### Secondary Effectiveness Endpoint

- Tremor power (kinematic response), as collected with the device during postural holds (outstretched or wing beating), change from pre-stimulation to post-stimulation across sessions.

This endpoint will be tested statistically using hypotheses as defined above.

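### Does the SAP need a written joint success rule for TETRAS and ADL, and a gate before the tremor-power test?

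*SAP*

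**What the plan says.** SAP 2.1 sets one level for every test: "two-sided test at a 0.05 level of significance or a one-sided test at a 0.025 level of significance". It gives no family-wise level. SAP 2.3 defines the two co-primaries, states the statistical objective for each of them, and says that "the null and alternative hypotheses to be tested for each primary endpoint are as follows": H0: μ_T ≥ 0 against HA: μ_T < 0. There μ_T is "the raw change in the rating score from pre-stimulation at baseline to post-stimulation at three months in the endpoint in question".

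SAP 2.7 repeats the co-primaries and adds: "These endpoints will be tested statistically using hypotheses as defined above and converted to percent tremor reduction". For the secondary endpoint, tremor power, it says: "This endpoint will be tested statistically using hypotheses as defined above". The quantity there is the "change from pre-stimulation to post-stimulation across sessions".

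The protocol synopsis uses the same co-primary and secondary labels, lists everything else as exploratory, and gives the size as "Up to 500 subjects". Neither document, as supplied, has a multiplicity section, a sentence joining the two co-primary results, or a testing order.

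**The concern.** Three formal tests share one per-test level, and nothing written links them. Two questions follow.

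- If TETRAS rejects and ADL does not, or the reverse, has the study succeeded? The reader has to infer the answer from the label and the objective.
- If a co-primary fails and tremor power gives a small p-value, is that a finding or a description?

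If these were settled after the data were seen, a mixed result could be presented in the more favourable way, and the chance of some false claim would exceed the nominal 2.5%. The secondary test also borrows a hypothesis written for another quantity: μ_T is a rating-score change over three months, whereas tremor power is a change around stimulation, taken across sessions.

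**Working it through.** **Inputs from the documents.** Two co-primaries (SAP 2.3), one secondary test (SAP 2.7), two-sided 0.05 or one-sided 0.025 per test (SAP 2.1), at most 500 subjects (protocol synopsis). The documents give no power, effect size or correlation. Those below are assumptions: equicorrelated normal test statistics with r = 0, 0.3, 0.6 and 0.9, each test rejecting when Z > 1.960 in the favourable direction.

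**1. The plan's own figure.** 0.05 / 2 = 0.025, and both forms have critical value 1.960. The two stated levels agree for a directional claim. There is no other error-rate figure to reproduce.

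**2. The primary claim with both scales required.** Let A and B be rejection on TETRAS and ADL. If at least one null holds, P(A and B) cannot exceed the smaller of P(A) and P(B), so it is at most 0.025. With both nulls true it is 0.025² = 0.0006 if the tests are independent and 0.0148 at r = 0.9. If one scale is almost certain to reject, it is 0.025 at every r. No alpha split is needed.

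**3. Adding tremor power (C) as a claim, without a gate.**

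P[(A and B) or C] = P(A and B) + P(C) − P(A and B and C)

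Under independence:

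- all nulls true: 0.000625 + 0.025 − 0.0000156 = 0.0256;
- A has 80% power, B and C null: 0.8 × 0.025 + 0.025 − 0.8 × 0.025² = 0.0445;
- A has power near 1: 1 − 0.975² = 0.0494.

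Numerical integration gives the correlated cases:

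| Situation | r = 0 | 0.3 | 0.6 | 0.9 |
|---|---|---|---|---|
| No gate, all three nulls true | 0.0256 | 0.0269 | 0.0285 | 0.0285 |
| No gate, one scale works with 50% power | 0.0372 | 0.0421 | 0.0427 | 0.0352 |
| No gate, one scale works with 80% power | 0.0445 | 0.0463 | 0.0437 | 0.0352 |
| No gate, one scale works with power near 1 | 0.0494 | 0.0476 | 0.0438 | 0.0352 |
| Gate, all three nulls true | 0.0006 | 0.0024 | 0.0062 | 0.0148 |
| Gate, one scale works with power near 1 | 0.0250 | 0.0250 | 0.0250 | 0.0250 |

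The 4.9% corner needs three things together: one scale nearly certain to succeed, no true change on the other scale or on tremor power, and independent tests. All three outcomes concern tremor or tremor-related disability of the same stimulated limb in the same subjects, so independence is the least plausible setting.

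**4. What a gate would do in practice.** It matters only when a co-primary fails. For 90% power per test, the mean change needed is (1.960 + 1.282) / √500 = 0.145 SD with 500 evaluable subjects, or (1.960 + 1.282) / √250 = 0.205 SD with an assumed 250. If every true change is 0.3 SD (assumed) and n = 250, power per test is Φ(0.3 × √250 − 1.960) = Φ(2.783) = 0.9973. Under independence, the chance of a tremor-power claim then falls by 0.9973 − 0.9973³ = 0.005. In that setting the gate almost never binds.

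**5. The borrowed hypothesis.** The direction carries over, because a fall in tremor power is the benefit. An analyst would read the null as a mean pre- to post-stimulation change of at least zero, which is how SAP 2.7 defines the endpoint.

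**The case for a change.** The case for adding the rules is reasonable. A label is not a decision rule, and the hypotheses are written one endpoint at a time. Tremor power is set apart from the exploratory list and given a formal test, so a reader may take its p-value as more than description. The remedy would cost two sentences and would fix the meaning of a mixed result before data are seen.

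Part of this stands. The supplied text does not state the joint rule or a gate. The reference back to μ_T is loose, and it leaves open how sessions are combined within a subject. That last point concerns the definition of the endpoint; it is not a question of multiplicity, and a gate would not answer it.

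The rest does not carry enough weight. SAP 2.3 sets the aim of showing a reduction for each primary endpoint, which supports the usual meaning of co-primary. No passage supports the reading that either scale alone would do, so no error rate should rest on it. For tremor power, the excess over 2.5% exists only if a secondary result is promoted to a claim, and nothing in the documents does that. There is also no stated family-wise level for the plan to breach.

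Two limits apply: the protocol was available only as a synopsis, and part of the SAP's text was removed before review, so a rule stated elsewhere cannot be excluded.

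**Conclusion.** No change follows. This is a gap in wording that analysts fill sensibly: both co-primaries are needed for success, and tremor power is reported as secondary. On that reading the primary claim is held at 2.5% or less without any adjustment. Writing the rules down would alter no estimate, p-value or primary conclusion.

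The excess is conditional and modest: 2.6–2.9% when all nulls hold, and 3.5–4.9% in a case built to be unfavourable (one scale with power near 1, the other two nulls exactly true, correlation from 0.9 down to 0). It would matter only if the sponsor meant to make a confirmatory tremor-power claim whatever the co-primaries showed, and the documents express no such intention. The conclusion rests on the ordinary meaning of co-primary and on tremor power staying secondary. It does not bear on the single-arm design, which is a separate question.

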### **2.4 Subject Disposition and Accountability**

Subject disposition will be presented in a table and flow diagram depicting the disposition of all enrolled subjects, including the number enrolled, the number who completed the study and the number and reasons of those who discontinued.

### **2.5 Demographics and Baseline Characteristics**

Demographic and baseline characteristics will be summarized and reported.

### **2.6 Poolability**

The study will be conducted at up to 40 investigational sites, with the intent of pooling the data for analyses. All sites will follow the same protocol, use the same data collection tools, and be given the same training. Every effort will be made to promote consistency in study execution across investigational sites.

### **2.7 Effectiveness Outcomes**

The effectiveness of the Cala TWO device in reducing essential tremor symptoms will be evaluated by the following:

Co-Primary Effectiveness Endpoints

---

- TRG Essential Tremor Rating Assessment Scale (TETRAS) subset score, relevant to the stimulated upper limb, raw change from pre-stimulation at baseline to post-stimulation at 3 months.
- Bain & Findley Activities of Daily Living (ADL) scale subset score, relevant to the stimulated upper limb, raw change from pre-stimulation at baseline to post-stimulation at 3 months.

These endpoints will be tested statistically using hypotheses as defined above and converted to percent tremor reduction as previously reported by Elble et. al. 2016.

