**PROSPECT: PROSPECTIVE STUDY FOR SYMPTOMATIC RELIEF OF
ESSENTIAL TREMOR WITH CALA THERAPY**

**PROTOCOL ET-14
REV A; 22 JUNE 2018**

Cala Health, Inc.
[name]
[name]

CLINICAL STUDY SYNOPSIS

| Study Objective | |
|------------------------|--|
| Title | PROSPECT: PROspective study for SymPtomatic relief of Essential tremor with Cala Therapy |
| Study Device | Cala TWO Device |
| Objective | The study objective is to evaluate symptomatic hand tremor relief in the treated hand following stimulation with the Cala TWO device in adults with essential tremor over a 3-month duration |

| Study Design Elements | |
|------------------------------|--|
| Study Design | Prospective, multi-center, single-arm, non-significant risk study designed to evaluate the Cala TWO device. Subjects will be screened for eligibility and fitted with a Cala TWO device. Subjects will wear the device at home for a period of 3 months, during which they will be asked to stimulate their dominant hand twice a day. The stimulation amplitude will be based on each subject's stimulation threshold. Subjects will have in clinic assessments at enrollment, month 1 and 3. |
| Effectiveness Endpoints | 
The effectiveness of the Cala TWO device in reducing essential tremor symptoms will be evaluated by the following:
 
Co-Primary Effectiveness Endpoints
 
 • TRG Essential Tremor Rating Assessment Scale (TETRAS) subset score, relevant to the stimulated upper limb, change from pre-stimulation at baseline to post-stimulation at 3 months. • Bain & Findley Activities of Daily Living (ADL) scale subset score, relevant to the stimulated upper limb, change from pre-stimulation at baseline to post-stimulation at 3 months. 
Secondary Effectiveness Endpoint
 
 • Tremor power, as collected with the device during postural holds, change from pre-stimulation to post-stimulation across sessions. 
Additional Exploratory Analyses
 
 • Quality of Life in Essential Tremor Questionnaire (QUEST) • Clinician/Patient Global Impression of Severity (C/PGI-S) • Clinician/Patient Global Impression of Improvement (C/PGI-I) • Patient Session Impression of Improvement (PSI-I) • TETRAS – subset relevant to non-stimulated upper limb • TETRAS and ADL pre- versus post-stimulation within each visit • Product Survey • Device usage metrics |

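### Does SAP 2.7 need to print the formula that turns the two co-primary changes into percent tremor reduction?

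*SAP*

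**What the plan says.** SAP 2.3 sets the hypotheses for each co-primary endpoint. The tested parameter "is the raw change in the rating score from pre-stimulation at baseline to post-stimulation at three months". SAP 2.7 repeats that both endpoints are raw changes in a subset score for the stimulated limb, then adds one sentence on a second way of expressing them: "These endpoints will be tested statistically using hypotheses as defined above and converted to percent tremor reduction as previously reported by" a 2016 publication.

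No other supplied section mentions a percentage conversion. The protocol synopsis defines the second co-primary simply as "Bain & Findley Activities of Daily Living (ADL) scale subset score, relevant to the stimulated upper limb, change from pre-stimulation at baseline", measured up to the 3-month visit after stimulation, and treats TETRAS the same way. The inclusion criteria set separate entry minima: for TETRAS "a minimum subset score of 6 across all upper limb items", for the ADL scale "a minimum subset score of 8 across all upper limb items". SAP 2.1 requires mean, standard deviation, median and quartiles for both scales.

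**The concern.** A percentage is easy to quote, and here it is a prespecified expression of effect for both co-primary endpoints. Yet the SAP prints no formula or coefficient. It does not say whether the method works on the subset total or an item average, or whether each subject is converted and then averaged or the group mean is converted once. Two analysts could report different percentages from the same data.

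The ADL scale adds a question of meaning. The protocol introduces it as a measure of disability: "Significant disability due to essential tremor (Bain & Findley score of 3 or above in any one of the upper limb items". If the cited method was built for tremor ratings only, the converted ADL figure would present a change in disability as a reduction in tremor. It would also stand beside a secondary endpoint that the device measures directly: "Tremor power (kinematic response), as collected with the device during postural holds".

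**Working it through.** The documents state no percent reduction, expected effect, standard deviation or power, so there is no figure of the plan's own to reproduce. The check has three parts.

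**1. What depends on the conversion**

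| Output | Where defined | Uses the percentage? |
|---|---|---|
| TETRAS test | SAP 2.3, 2.7 | No, raw change |
| ADL test | SAP 2.3, 2.7 | No, raw change |
| Means, SDs, medians, quartiles of both scales | SAP 2.1 | No |
| Percent tremor reduction, TETRAS and ADL | SAP 2.7 | Yes |

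So 0 of 2 tests and 2 of 2 converted figures are affected.

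**2. What the SAP sentence settles**

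- *Which scales:* settled. The sentence follows both bullets and refers to both, so one cited method serves both.
- *Starting input:* partly settled. What is converted is the raw change in the subset score; how the method scales it lies in the citation.
- *Number of items:* fixed by the scale subset, not by the analyst.
- *Coefficient:* would come from the cited method, which cannot be consulted here.
- *Level (per subject or group mean):* not stated in the SAP.
- *Basis for ADL:* not stated in the SAP.

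**3. How far the figure could move**

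Assumptions, none from the documents or the cited source: mean drop 2 points; SD of change 3; *m* = 4, 6 or 8 items; amplitude changing by a factor *k* = 1.5, 2 or 3 per rating point.

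Two wide spreads can be produced:

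- Percent of baseline score: 2/6 = 33.3%, 2/12 = 16.7%, 2/18 = 11.1% on TETRAS; 2/8 = 25.0% at the ADL entry minimum.
- Log-linear on the item average, 1 − *k*^(−2/*m*): from 9.6% (*k* = 1.5, *m* = 8) to 42.3% (*k* = 3, *m* = 4).

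Neither measures analyst freedom. The first varies the baseline, which is data. The second varies *k* and *m*, which the cited method and the scale would fix.

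Holding the method fixed and varying only the level of application:

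| Method | Group mean | Per subject, then averaged |
|---|---|---|
| Percent of score, baseline uniform 6 to 18 | 2/12 = 16.7% | 2 × ln(18/6)/12 = 18.3% |
| Percent of score, baselines 6, 12, 18 equally common | 2/12 = 16.7% | (33.3 + 16.7 + 11.1)/3 = 20.4% |
| Log-linear, *k* = 2, *m* = 6, normal change | 1 − 2^(−2/6) = 20.6% | 1 − 2^(−2/6) × exp[(3 ln 2/6)²/2] = 15.7% |

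For scale, the sampling half-width at 500 subjects is 1.96 × 3/√500 = 0.263 points. At baseline 12 that gives (2 ± 0.263)/12, or 14.5% to 18.9%. For the log-linear group mean it gives 18.2% to 23.0%. The protocol's figure is a ceiling ("Up to 500 subjects"). At 100 subjects the half-width is 1.96 × 3/√100 = 0.588 points, and the intervals are 11.8% to 21.6% and 15.1% to 25.8%.

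The 18.3% lies inside its interval at both sizes. The 20.4% and the 15.7% lie outside at 500 and inside at 100. Whether the level matters beyond sampling error therefore depends on the assumed method, the spread of baselines and the number enrolled.

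**The case for a change.** The best case for a change is that it costs one short paragraph and makes a quotable figure reproducible. Even if the publication fixes the formula and coefficient, the SAP does not state the level of application. Under the log-linear assumption at 500 subjects, the per-subject figure (15.7%) falls below the whole interval of the group-mean figure (18.2% to 23.0%). The SAP also gives no reason for calling a change on a disability scale a tremor reduction.

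The textual point stands: the formula, the level and the ADL basis are not printed. The harm does not follow from it. Naming one dated publication is weaker than printing its equation, but it ties the analyst to a method before the data. The publication may settle the level as well; that cannot be known from the documents. The same holds for ADL. SAP 2.3 itself treats both scales as showing that essential tremor is reduced, and different entry minima say nothing about whether a conversion is valid. To say that the ADL figure would mislead, one would need the source.

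**Conclusion.** No change to the plan follows. This is missing detail in a supplementary figure, and analysts can fill it sensibly: they apply the cited method and state the formula and level beside the result. Printing these in the SAP would help reproducibility but would alter no test, p-value or raw summary, and readers will have the raw-score results whatever conversion is used.

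Under the assumed 2-point drop and SD of 3, the level of application moves the percentage by 1.6 to 4.9 points (16.7% to 18.3%, 16.7% to 20.4%, or 20.6% to 15.7%). These sizes rest on assumed methods and baselines, not on the cited source. The conclusion does not depend on them: it rests on the tests being defined on raw change and on the SAP naming a single published method. It is limited to the supplied text, in which the protocol appears as a synopsis and part of the SAP was removed. Whether the cited method suits the Bain & Findley ADL subset remains unjudged.
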